### **10.8 Ad hoc data reviews**

Ad hoc data reviews of unblinded data may be conducted by a Sponsor team during the conduct of the study to support decision-making concerning the current study or the Sponsor's clinical development program in general. These reviews will be conducted by a limited Sponsor team not involved in the conduct of the study during the randomized period of the study.

## **11 Ethical considerations**

### **11.1 Regulatory and ethical compliance**

This clinical study was designed and shall be implemented, executed and reported in accordance with the ICH Harmonized Tripartite Guidelines for GCP, with applicable local regulations (including European Directive 2001/20/EC, US Code of Federal Regulations Title 21, and Japanese Ministry of Health, Labor, and Welfare), and with the ethical principles laid down in the Declaration of Helsinki.

### **11.2 Responsibilities of the investigator and ethics committee**

Before initiating a trial, the Investigator/institution must obtain approval/favorable opinion from the ethics committee (EC) for the trial protocol, written informed consent form, consent form updates, patient recruitment procedures (e.g., advertisements) and any other written information to be provided to patients. Prior to study start, the Investigator is required to sign a protocol signature page confirming his/her agreement to conduct the study in accordance with these documents and all of the instructions and procedures found in this protocol and to give access to all relevant data and records to [REDACTED] monitors, auditors, [REDACTED] Quality Assurance representatives, designated agents of Anthos Therapeutics, ECs, and regulatory authorities as required. If an inspection of the clinical site is requested by a regulatory authority, the Investigator must inform Anthos Therapeutics or a delegate working on their behalf immediately that this request has been made.

For multi-center trials, a Coordinating Investigator will be selected by Anthos Therapeutics or a delegate working on their behalf around the time of Last Patient Last Visit to be a reviewer and signatory for the CSR.

### **11.3 Publication of study protocol and results**

The key design elements of this protocol will be posted in a publicly accessible database such as clinicaltrials.gov. Upon study completion and finalization of the study report the results of this trial will be posted in a publicly accessible database of clinical trial results in accordance with local regulations.

No publication or disclosure of study results will be permitted except under the terms and conditions of a separate written agreement between the Sponsor and the Investigator and/or the Investigator's institution. A Publication Committee, led by the TIMI Study Group, will oversee publication of primary and secondary results. Further details of the composition, roles, responsibilities, and processes of the Publication Committee will be documented in the Publication Committee Charter.

The information developed from this clinical study will be used by the Sponsor in connection with the development of abelacimab and other drugs and diagnostics, and thus may be disclosed

as required to other clinical investigators, business partners, or regulatory agencies. To permit the information derived from the clinical studies to be used, the Investigator is obligated to provide the Sponsor with all data obtained in the study.

## **12 Protocol adherence**

This protocol defines the study objectives, the study procedures, and the data to be collected on study participants. Additional assessments required to ensure safety of patients should be administered as deemed necessary on a case by case basis. Under no circumstances is an investigator allowed to collect additional data or conduct any additional procedures for any research related purpose involving any investigational drugs under the protocol.

Investigators ascertain they will apply due diligence to avoid protocol deviations. If an investigator feels a protocol deviation would improve the conduct of the study this must be considered a protocol amendment, and unless such an amendment is agreed upon by Anthos Therapeutics and approved by the EC and health authorities, where required, it cannot be implemented.

### **12.1 Protocol Amendments**

Any change to the protocol can only be made in a written protocol amendment that must be approved by Anthos Therapeutics, Health Authorities where required, and the IRB prior to implementation.

Amendments that are intended to eliminate an apparent immediate hazard to patients may be implemented immediately, provided the Health Authorities are subsequently notified by protocol amendment and the reviewing EC is notified.

Notwithstanding the need for approval of formal protocol amendments, the Investigator is expected to take any immediate action required for the safety of any patients included in this study, even if this action represents a deviation from the protocol. In such cases, the reporting requirements identified in [Section 8](#) (Safety Monitoring) must be followed and the Study Lead informed.

## 14 Appendix 1 – Components of the CHA2DS2-VASc Score

Table 14-1 Components of the CHA2DS2-VASc Score (Lip et al 2010)

	Item	Points
C	Congestive heart failure (or left ventricular systolic dysfunction)	1
H	Hypertension: blood pressure consistently above 140/90 mmHg (or treated hypertension on medication)	1
A 2	Age $\geq 75$ years	2
D	Diabetes Mellitus	1
S 2	Prior Stroke or TIA or systemic arterial thromboembolism	2
V	Vascular disease (e.g., peripheral artery disease, myocardial infarction, aortic plaque)	1
A	Age 65–74 years	1
Sc	Sex category (i.e., female sex)	1

## 15 Appendix 2 – Management of Bleeding

The management of suspected bleeding is at the discretion of the Investigator and will depend on the source/location of the bleeding and the severity. In all cases of bleeding, the Investigator should use clinical judgment in assessing the risk to the patient and monitor whether the bleeding is resolving or worsening.

See below for suggested guidance for patients randomized to abelacimab or rivaroxaban. Regardless of study drug assignment, in the event of severe or life-threatening bleeding such as bleeding resulting in hemodynamic compromise requiring intervention (such as endoscopy, angiography, or surgery) or an intracranial hemorrhage, the following steps should be considered:

- Withhold study drug and all antiplatelet agents / open label anticoagulants
- Institute standard of care for life-threatening bleeding (e.g., large bore i.v. or central venous access, type and crossmatch blood, admit to the intensive care unit, and provide hemodynamic and respiratory support, as needed)
- Administer packed red blood cells (or whole blood) as needed
- Consider measures specific to the patient's study treatment as described below

In cases of severe or life-threatening bleeding, the investigator is encouraged to contact the [REDACTED]  
[REDACTED]

### 15.1 Abelacimab

Management of active bleeding in patients administered abelacimab should begin, if possible, with local measures (e.g., pressure or packing) at the site to control any bleeding, if possible. Minor bleeding events, such as epistaxis or superficial bleeding, can usually be managed conservatively using local measures without interruption of study drug treatment. As noted above, treatment of moderate to severe bleeding may require intravenous fluid replacement and blood transfusions. There is currently no specific reversal agent for abelacimab. Investigators are encouraged to call the [REDACTED] for further guidance.

Based on clinical experience managing FXI deficient individuals, treatment options for patients randomized to abelacimab include anti-fibrinolytic agents such as tranexamic acid (TXA), topical hemostatic agents such as fibrin glue, and pro-hemostatic blood components such as low dose recombinant activated factor VII (rFVIIa), prothrombin complex concentrate (PCC), fresh frozen plasma (FFP), and activated PCC [e.g., factor VIII inhibitor bypass activity (FEIBA)].

Of note, FXI concentrates are available in some countries (not marketed in the US); however, FXI concentrates are not likely to be effective in patients on abelacimab because the excess free abelacimab antibody in the circulation is expected to quickly neutralize the exogenous FXI.

Antifibrinolytic agents have been used extensively in FXI deficient patients. Since bleeding in FXI deficient patients typically occur in areas of high fibrinolytic activity such as the oral mucosa, nasal mucosa, and urinary tract, procedures such as dental extractions can be performed with oral antifibrinolytic therapy alone starting the night before and continuing for 7 days (Duga et al 2013). Tranexamic acid (TXA) is the most frequently used agent and can be given orally as a tablet or a 5% mouthwash, as well as intravenously. Fibrin glue has also been used to restore local hemostasis during dental surgery in patients with FXI deficiency (Duga et

al 2013) and is an option for patients administered abelacimab.

TXA, fibrin glue, and rFVIIa alone or in combination have been used to treat serious bleeding in FXI deficient patients undergoing major surgery and may be considered in the event of severe or life-threatening bleeding in patients administered abelacimab. Studies show that a regimen of low-dose rFVIIa at a dose of 30 µg/kg followed by administration of rFVIIa at a dose of 15–30 µg/kg every 2–4 hours for 24–48 hours in addition to TXA 1 g every 6 hours for 5 to 7 days can bypass the effect of FXI deficiency, restore coagulation parameters, and prevent serious bleeding after major surgery in FXI deficient patients (Riddell et al 2011, Livnat et al 2009).

*In vitro* thromboelastometry studies showed that rFVIIa is capable of bypassing the inhibition of FXIa produced by abelacimab in human blood and in plasma from cynomolgus monkeys. In blood from healthy human donors, the prolongation of clotting time induced by abelacimab was shortened upon addition of rFVIIa (see abelacimab IB). Recombinant FVIIa carries a boxed warning for thrombosis, so this therapy should only be used in cases of severe bleeding where the treating physician judges the benefit-risk to favor treatment with rFVIIa.

As a last resort, therapeutic plasmapheresis to remove abelacimab may be an option where definitive removal of abelacimab is required. Therapeutic plasmapheresis using FFP in exchange of patient's own plasma to remove free and total abelacimab and to restore FXI to desired levels in life-threatening bleeding could lead to definitive neutralization of the PD effects of abelacimab if necessary. Clinical experience with this approach, however, is currently lacking.

## 15.2 Rivaroxaban

Active bleeding in patients randomized to rivaroxaban should be managed according to local standard of care and guidelines (Hindricks et al 2020).

Active bleeding in patients administered rivaroxaban should begin with local measures (e.g., pressure or packing) at the site to control any bleeding, if possible. Minor bleeding events, such as epistaxis or superficial bleeding, can usually be managed conservatively without interruption of study drug treatment.

As noted above, treatment of moderate to severe bleeding may require intravenous fluid replacement and blood transfusions. If the last dose of rivaroxaban was within 2–4 hr, the use of activated charcoal may be considered to reduce further exposure. Specific treatment interventions to identify and manage the cause of bleeding (e.g., gastroscopy) should be performed promptly.

In cases of severe or life-threatening bleeding, reversal of the effects of rivaroxaban with andexanet alfa can be considered to restore physiological hemostasis. If unavailable, general hemostatic agents, such as 4-factor prothrombin complex concentrates (PCC) may be used. Activated prothrombin complex concentrates (aPCC), or rFVIIa can be considered; however, these can also increase the risk of thrombosis.

Investigators are encouraged to call the [REDACTED] for further guidance.

## 16 Appendix 3 – Assessment Schedules

**Table 16-1 Assessment Schedule (Year 1)**

Period	Screening	Treatment Period (Year 1)													
		Day				Month									
		-30 to -1	1	8	30	60	3	4	5	6	7	8	9	10	11
Visit Window (days)				±2	±3	±3	±5	±5	±5	±5	±5	±5	±5	±5	±5
Informed consent/Genetic consent 	x														
Inclusion/Exclusion criteria	x	x													
Demography/Medical History	x														
Physical Exam	s														
Height and Weight	x														
Vital signs	x	x		x					x						x
12-lead ECG	x														
HIV, Hepatitis B, Hepatitis C	s														
Serum Pregnancy and FSH	x														
Urine Pregnancy - WOCBP only		s		s		s		s		s		s		s	
Hematology	x	x				x		x		x		x		x	
Chemistry	x							x							x
Urinalysis	x														
PT/INR, aPTT	x	x		x		x		x		x		x		x	
PK  and Free FXI / Total FXI 		x		x		x		x		x		x		x	
Antidrug antibodies (ADA) 		x		x		x		x		x		x		x	
Factor XI Coagulation Activity 		x		x		x		x		x		x		x	
Exploratory biomarkers 	x														x
Genetic sample 	x														
EQ-5D-5L and ACTS PROs 	x							x							x
Telephone call visit only			x												
Study drug s.c. administration 		x		x	x	x	x	x	x	x	x	x	x	x	x
Study drug p.o. accountability 			x	x	x	x	x	x	x	x	x	x	x	x	x
Injection site inspection 		x		x	x	x	x	x	x	x	x	x	x	x	x
Concomitant medications	x								x						
AE assessment								x							

 The genetic informed consent is for an optional sub-study; the genetic sample can be collected at any time after the optional genetic informed consent is obtained

 Only collected from patients assigned to abelacimab

 May be collected in a subset of patients

 Patients assigned to abelacimab only; Dose can be administered at in-clinic or in-home visits by medically qualified, un-blinded study staff or designees as locally permitted. If administered in-home, assessments for concomitant medications, AEs, and other changes in health status will be conducted by sites via telephone or video call as locally permitted

 Patients assigned to rivaroxaban only; Accountability can be assessed at in-clinic visit or via virtual (e.g. video call) visit as appropriate and locally permitted

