**Table 3-1 Transition Guidelines**

Baseline anticoagulant therapy	Instructions
Direct oral anticoagulant (DOAC)	The patient's last dose of DOAC should be approximately 12-24 hours prior to receiving study medication on Day 1.
Vitamin K antagonist (VKA)	After enrolled and found to be eligible, patients should have their VKA discontinued, and INRs should then be performed every 1 to 2 days based on initial INR. The patient should be randomized as soon as possible (ideally within 36 hours) once the INR is <2.5. Sites may collect repeat INR samples using point of care devices or send for local analysis, in which case results will remain as part of source documentation only.

Eligible patients will be randomized into one of the following treatment groups:

- Treatment group 1: abelacimab 90 mg s.c. monthly
- Treatment group 2: abelacimab 150 mg s.c. monthly
- Treatment group 3: rivaroxaban 20 mg p.o. once per day with the evening meal  
[Note: Patients with a CrCl  $\leq$ 50 ml/min by the Cockcroft-Gault equation will receive the 15 mg p.o. daily dose of rivaroxaban]

Patients will be randomized on Day 1, which will be the date of the first administration of study drug. Patients will be contacted by phone on Day 8 for a general health and safety check. Patients will be assessed for AEs and changes in concomitant medication every month during the study treatment period; patients assigned to abelacimab will receive their s.c. injection and patients assigned to rivaroxaban will have study medication compliance assessed during these monthly visits. Every third month, these visits will include additional safety assessments and collection of blood samples for laboratory analysis.

Where permitted, visits as indicated in the Assessment Schedule (Appendix 3), may be conducted at home by staff qualified to administer s.c. injections or by telephone/video-call, depending on treatment arm. In the case of visits conducted in the patient's home, with the patient's consent, the Investigator and/or delegated staff will arrange for the service and will provide the patient's name and address to the personnel conducting the in-home visit, which will be either site staff or locally contracted agency staff.

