### **6.4 Treating the patient**

#### **6.4.1 Dispensing the study drug Abelacimab**

Each study site will be supplied with abelacimab as single-use vials via the IxRS system. A unique kit number is printed on the vial label which corresponds to the abelacimab treatment

arm. Investigator staff will identify the study drug vial to be used for the patient by contacting the IxRS and obtaining the kit number containing that vial.

At the Day 1 and Day 30 visits, abelacimab will be administered to the patient by qualified medical personnel at the study center via s.c. injection as specified in the Pharmacy Manual. For these first two doses, patients must remain at the study center for at least 1 hour after administration of study drug to monitor for any ISRs, hypersensitivity reactions, or other AEs. Starting with the third dose, patients will either return to the study center every month to receive s.c. administration of study drug or opt to have study drug administered outside the study center by a visiting nurse or other assigned individual qualified to administer s.c. study medication (or a combination of visit scenarios depending on patient and site availability).

Patients participating in the extension period that received rivaroxaban or abelacimab 90 mg in the randomized period should be monitored as described above after the first dose of abelacimab 150 mg.

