### 6.8.1 Risks associated with the COVID-19 pandemic

The study treatments, including abelacimab, are not expected to alter the natural defense mechanisms or developing immunity to COVID-19. Anticoagulation therapy may have beneficial effects in preventing thromboembolic complications of COVID-19.

The COVID-19 pandemic may present added challenges for trial participants who may risk exposure to COVID-19 during travel to research centers and interactions with research staff. In order to minimize risk to trial participants, only critical study tasks were maintained. Furthermore, study procedures were designed to be adaptable to changing conditions related to the COVID-19 pandemic.

Investigators should make every effort to ensure that they are following local guidelines to prevent the spread of COVID-19 as well as provide appropriate medical oversight to patients enrolled into this study, whether visits are taking place on-site or using one of the flexible options that are available including:

- In-home visits in lieu of on-site visits for the s.c. administration of abelacimab;
- remote (via telephone or video-calls) visits in lieu of on-site visits when s.c. administration of abelacimab is not required;
- IXRS dispensing of multiple months of rivaroxaban supplies rather than requiring rivaroxaban patients to return to the site to obtain these supplies every month, as well as direct-to-patient shipment (from site to patient's home) of rivaroxaban supplies as needed and locally permitted.

If a patient contracts COVID-19 while enrolled in the study, the patient should be managed according to usual medical practice. COVID-19 should be recorded in the adverse events page.

Vaccination for COVID-19 is permitted during the study course.

Patients should not receive their injection of abelacimab within 3 days of receiving a COVID-19 vaccine.

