#### 6.8.4.3 Potential risk associated with

#### 6.8.4.4 Potential risk associated with s.c. injection

Injection site reactions can result in hematoma, hemorrhage, bruising, erythema, discoloration, swelling and edema formation, particularly following s.c. administration. The first and second injections of the study drug will be administered at the study site where patients will be monitored for injection site reactions.

A therapeutic strategy for the management of injection site reactions is provided in [Section 8.3](#).

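### The assessment schedule permits any abelacimab dose at home, while Section 6.4.1 requires on-site dosing and observation for the first two doses and the same monitoring after a first 150 mg extension dose; the texts need reconciling

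*Protocol*

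**What the plan says.** **The restrictive text.** Protocol Section 6.4.1 states: "At the Day 1 and Day 30 visits, abelacimab will be administered to the patient by qualified medical personnel at the study center". It continues: "For these first two doses, patients must remain at the study center for at least 1 hour after administration of study drug". The purpose it gives is to watch for injection site reactions, hypersensitivity and other adverse events. Administration outside the centre is offered from the third dose. For the extension, the same section asks that patients coming from rivaroxaban or from 90 mg be monitored in the same way after their first 150 mg dose. Section 6.8.4.4 agrees on place: "The first and second injections of the study drug will be administered at the study site". It mentions monitoring for injection site reactions but gives no duration.

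**The permissive text.** In Table 16-1 the row "Study drug s.c. administration" is marked at Day 1, Day 30, Day 60 and each later month, and carries footnote 4: "Dose can be administered at in-clinic or in-home visits by medically qualified, un-blinded study staff or designees as locally permitted". The footnote goes on: "If administered in-home, assessments for concomitant medications, AEs, and other changes in health status will be conducted by sites via telephone or video call". Table 16-2 repeats the footnote on a row that is also marked at the EoT visit. Section 3.1.2 says that visits shown in Appendix 3 "may be conducted at home by staff qualified to administer s.c. injections", where permitted and depending on the arm. Section 6.8.1, on COVID-19, lists among its flexible options: "In-home visits in lieu of on-site visits for the s.c. administration of abelacimab".

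**The concern.** Section 5 and Section 3.1.2 both send sites to the assessment schedule, so it is the page that staff are likely to work from. That page does not carry the limit on the first two doses. For a home dose it describes remote assessment of adverse events and mentions no observation period.

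What could be lost is a safeguard that the protocol set for itself. Sections 6.8.4.2 and 8.3.1 say that immediate hypersensitivity reactions appear in the first hours after administration, and 8.3.1 adds that acute anaphylaxis could be life-threatening. A telephone or video assessment is not the stay at the centre that 6.4.1 describes.

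**Working it through.** The plan states no figure to reproduce, and no power or event calculation enters. The check is a comparison of texts.

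| Source | Place of doses 1 and 2 | Observation afterwards | First dose allowed off site |
|---|---|---|---|
| Section 6.4.1 | Study centre | At least 1 hour at the centre, mandatory | Third |
| Section 6.8.4.4 | Study site | Monitoring, no duration | Not stated |
| Table 16-1, footnote 4 | Clinic or home | None stated; remote assessment if at home | First |
| Section 3.1.2 | Refers to Appendix 3 | Not stated | As the schedule |
| Section 6.8.1 | Home offered, no exception | Not stated | Not limited |

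**Step 1: extent of the disagreement.** Section 6.4.1 bars off-site administration for two randomized-period doses (Day 1 and Day 30). Footnote 4 bars it for none. The texts differ on 2 − 0 = 2 doses per abelacimab patient. No text says which source prevails.

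**Step 2: what a site using only the schedule would omit.** Footnote 4 also sits on the injection site inspection row, which is marked at Day 1 and Day 30. That check stays scheduled. What could drop out is the observed stay at the centre, and its 1-hour length appears only in 6.4.1.

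**Step 3: whether those doses were still to come.** Section 1.2.2 reports 1,287 patients randomized 1:1:1 and enrollment complete in December 2021. It puts mean time on treatment above 12 months by September 2022. With an exact two-thirds split, 1,287 × 2/3 = 858 patients were assigned to abelacimab. If each received both doses, 858 × 2 = 1,716 first and second injections were given. That is a ceiling on past doses, and it says nothing about how many were given at home.

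**Step 4: what remained ahead under this version.** Section 3.1.3 makes the EoT visit Day 1 of the optional extension, and Table 16-2 marks s.c. administration at EoT under the unrestricted footnote 4. Section 6.4.1 asks for monitoring after the first 150 mg dose in patients from two of the three arms, and those from rivaroxaban would be receiving abelacimab for the first time. On the same split, the ceiling is again 1,287 × 2/3 = 858 patients. The true number is smaller to the extent that patients had stopped treatment, did not qualify or consent, or were at sites that did not take part. The monthly doses in Table 16-2 are Year 2 doses and would not ordinarily be a first or second dose, so only its EoT column matters here. The content of the extension schedule (Table 16-3) is not available to check.

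**The case against.** The strongest reply is that the texts can be obeyed together. Footnote 4 is a general permission, and Section 6.4.1 is a specific and mandatory limit. A site that doses in clinic breaks neither, and 6.4.1 describes the same home option from dose three, so the footnote can be read as shorthand for it. Day 1 is in practice a site visit: eligibility is confirmed, the IxRS is contacted for randomization, and vital signs and bloods are taken. Section 6.8.1 is a pandemic risk section, not the dosing instruction. Home doses are given by medically qualified staff, and a safety call follows on Day 8. The Pharmacy Manual, which 6.4.1 cites for administration, may also settle the matter, but it is not available here.

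Most of this stands, and it rules out three stronger readings that a reader might infer:

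- **That a site following the schedule skips the monitoring.** The footnote permits home dosing and does not require it. The omission needs a site to use the home option at Day 1 or Day 30 and to overlook 6.4.1.
- **That some 1,716 injections are under conflicting instructions now.** Under this version they were already past. Wording in force during enrollment is not shown, and the number given at home could be zero.
- **That early reactions were observed unevenly across sites.** The documents report nothing either way.

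The reply does not remove the conflict itself. Reading the two texts together works only for someone who has both in view, and Section 3.1.2 points to the schedule. Day 30 has no randomization or eligibility check to hold it at the site. For the extension dose, 6.4.1 states the monitoring, but the footnote on the EoT column again has no exception.

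**Conclusion.** The conflict is real and narrow. The schedule allows every abelacimab dose at home, whereas 6.4.1 and 6.8.4.4 place the first two at the site, with an observed stay in 6.4.1. A site relying on the schedule alone could omit that observation.

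The size is two doses per abelacimab patient in the randomized period, already past under this version, and one dose at Extension Day 1 for patients coming from rivaroxaban or 90 mg if the extension opens. How many doses were or would be given at home is unknown. The counts in the working are ceilings that assume an exact 1:1:1 split and full dosing.

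Two limits apply. Table 16-3 cannot be checked and may already deal with the extension dose. The SAP addendum also postdates a final database lock of 8 March 2024, so Extension Day 1 doses may by then be past as well; the documents do not say how many patients entered.

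The primary endpoint, its analysis and the event target are not affected. This is a safety-instruction point that should be corrected because the omitted step is one the protocol makes mandatory.

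**What to change.** Reconcile footnote 4 of Tables 16-1 and 16-2 and Sections 3.1.2 and 6.8.1 with Sections 6.4.1 and 6.8.4.4, so that all state one rule on where the first two injections are given and what observation follows. State the rule for the first 150 mg extension dose in the same way, at the EoT column of Table 16-2 and in Table 16-3. Which rule applies is for the sponsor to decide.

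Until the text is amended, tell sites in writing which passage governs.

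The cost is wording in the table footnotes and the sections named, plus one site communication. No change to data collection, sample size or analysis is needed.
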